### **Setting**

Patients between 18 and 90 years of age, scheduled to undergo elective, primary total hip arthroplasty surgery at Davie Medical Center performed by the two orthopedic surgeons who perform THA by an anterior approach at our institution, will be identified for eligibility. These patients will be seen in the preoperative assessment clinic per our standard protocol prior to their surgery date, at which time the study will be discussed with all eligible patients, and they will be offered the ability to enroll in the study. Written informed consent will either be obtained during this visit, or the patient will be allowed to take the consent form home with them to discuss with their family and consider participation, and written informed consent can be finalized on the day of surgery.

## **Study Protocol**

### **Baseline data collection**

Upon arrival and check-in to the regional anesthesia area of surgical services at Davie Medical Center on the day of surgery, enrolled patients will be asked to rate their baseline verbal pain score both at rest and with movement on the eleven-point NRS pain scale (0-10, where 0 represents no pain and 10 represents the worst imaginable pain). Patient characteristics will be recorded, including age, gender, height, weight, BMI, surgeon, and operative side, as well as preoperative opioid use and doses. Baseline motor function will be assessed by straight leg raise on the surgical side to resistance and measured on the six-point Medical Research Council (MRC) scale (0-5, where 0 represents no voluntary contraction possible, 1 represents muscle flicker without movement of limb, 2 represents active movement only with gravity eliminated, 3 represents movement against gravity but without resistance, 4 represents movement possible against some resistance, and 5 represents normal motor strength against resistance).

Two phone numbers will be obtained from the patient, if the patient consents, for contact after discharge. Each patient will also be provided with a pain journal with which to document pain scores for any remaining time points after discharge, in case they are not available by phone at the time points of interest. All patients will still be admitted at the six hour mark, for collection of the primary endpoint of NRS pain with movement, as well as motor strength at six hours after block placement.

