**Summary/Purpose/Rationale**

Regional anesthesia procedures represent a common modality for postoperative analgesia after total hip arthroplasty surgeries (THA). The standard practice at our institution for many years has been the Lumbar Plexus block (LPB), which anesthetizes the L1-L5 lumbar nerve roots. While the LPB offers analgesia from the associated sensory block, it also blocks motor fibers, leading to lower extremity weakness that could potentially delay the patient's ability to participate in early physical therapy and may thereby delay discharge. In the past several years, newer regional anesthesia block approaches have been described and investigated in an attempt to provide patients with postoperative analgesia while avoiding associated muscle weakness, facilitating earlier physical therapy participation and discharge. One such nerve block is the peri-capsular nerve group (PENG) block, which anesthetizes the articular branches of the femoral, obturator, and accessory obturator nerves providing sensory innervation to the hip joint capsule without consistently causing lower extremity weakness. While we continue to perform LPB for postoperative analgesia after THA at our institution, some institutions are utilizing the PENG block to provide postoperative analgesia and facilitate early mobilization. There are currently no prospective studies that directly compare the efficacy of LPB to PENG block for providing postoperative analgesia after THA.

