**Objectives**

The purpose of this randomized, double blinded, prospective study is to compare the postoperative analgesia provided by the PENG block to that provided by the LPB for patients undergoing primary anterior approach THA. We hypothesize that the PENG block will provide equivalent analgesia to LPB after THA. The primary outcome will be a comparison of patient-reported numeric rating scale (NRS) pain scores with movement at six hours following block placement. Equivalency will be defined as a difference of less than one point in either direction on the eleven-point NRS pain scale (0-10). Secondary outcomes will include NRS pain scores with movement at 12, 18, and 24 hours, NRS pain scores at rest at 6, 12, 18, and 24 hours, time to first opioid administration, cumulative dose of postoperative opioid administration within the first 24 hours, motor strength at six hours after block placement as assessed by straight leg raise on a six-point scale (0-5), and distance walked at first postoperative physical therapy session. The 18 hour assessment for pain at rest and with movement is allowed to be done retrospectively at the time of the 24 hour assessment, as this time point would end up interrupting the sleep of the study subject as would be occurring in the early morning hours. If the subject reports asleep

at the 18 hour scheduled time point, the no pain score will be obtained. This will be considered a missing data point and not a deviation. If the subject reports they were awake at the 18 hour time point, then a pain score at rest will be obtained but if the subject reports no movement, this score will be a missing data point and not a deviation.

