### **Selection Criteria**

Inclusion: Adults between 18 and 90 years of age undergoing elective primary total hip arthroplasty surgery by an anterior approach at Atrium Health Wake Forest Baptist Davie Medical Center, and who have consented to and lack any contraindications to either LPB or PENG block for postoperative analgesia will be recruited for participation in the study.

Exclusion: Patients with any contraindications to regional anesthesia, such as history of allergy to amide local anesthetics, pre-existing coagulopathy or thrombocytopenia (less than 100,000 per microliter), refusal to either analgesic block, presence of a progressive lower extremity neurological deficit, localized or systemic infection, chronic use of high dose opioid analgesics (defined as daily use greater than 60mg oxycodone equivalents), as well as those who are pregnant, will be excluded from participation. A diagnosis of multiple sclerosis and Parkinson's disease will also exclude potential study subjects. Any patients who refuse enrollment or withdraw their consent will be excluded and any of their information already collected will be destroyed.

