Nurses will chart vital signs and medication administration in the electronic medical record (EMR) as per our standard protocol. Research personnel will measure patient-reported NRS pain scores at rest and with movement for each time by patient interaction, either face to face, or by calling the patient's room or phone numbers. This will include the primary outcome of patient-rated pain with movement of the surgical extremity on the NRS pain scale at six hours after block placement (roughly correlating to two hours after arrival to their room) as well as secondary outcomes that include but are not limited to pain at rest and with movement at 12, 18, and 24 hours following block placement, and strength to straight leg raise at six hours post-block placement. The cumulative 24 hour opioid consumption will be abstracted from the EMR for doses received while admitted, and documented by the patient in their pain journal and abstracted via phone call after their discharge, if this occurs prior to 24 hours after the block. Physical therapists will also document their encounters in the EMR, including but not limited to the secondary outcome of distance ambulated during their first session in feet. These metrics will be accessed, abstracted, de-identified, and analyzed by research personnel who are blinded to group allocation.

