### **Data Analysis**

Demographic information will be collected and compared between the groups to verify that randomization balanced out important baseline variables between LPB and PENG. For the primary outcome of patient-reported pain with movement at six hours after block placement, the equivalence hypothesis test of LPB versus PENG groups will be performed using two one-sided t-tests. We will also calculate a point and confidence interval estimate of the difference between LPB and PENG groups. Secondary outcomes will also be compared using t-tests and confidence intervals.

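### Six-hour strength: a straight leg raise cannot establish MRC grade 2, so the size of the mean difference depends partly on labelling, and the recorded baseline grade is not used in the analysis

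*Combined protocol and SAP*

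**What the plan says.** Baseline data collection gives the manoeuvre and the scale. "Baseline motor function will be assessed by straight leg raise on the surgical side to resistance", on the six-point MRC scale, where "2 represents active movement only with gravity eliminated, 3 represents movement against gravity but without resistance". Grade 0 is no voluntary contraction, and grade 1 is a flicker without limb movement. Objectives lists six-hour strength by straight leg raise on the same 0-5 scale as a secondary outcome, and Measurements repeats it as "strength to straight leg raise at six hours post-block placement". No section describes a gravity-eliminated position or says how to grade a patient who cannot raise the leg.

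On analysis, the Data Analysis section says "Secondary outcomes will also be compared using t-tests and confidence intervals". It names no baseline covariate, change score or ordinal method for strength. Its only stated use of baseline data is a balance check: "Demographic information will be collected and compared between the groups to verify that randomization balanced out important baseline variables".

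Randomization states that patients and the research personnel who collect outcomes are blinded to assignment.

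**The concern.** A straight leg raise is a lift against gravity. It can separate grades 3, 4 and 5. It cannot show movement that occurs only with gravity eliminated, which is the protocol's own definition of grade 2. When a patient fails to lift the leg, one assessor may record 2 and another 1 or 0 for the same limb. A t-test treats those labels as evenly spaced numbers, so the choice enters the mean.

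Motor sparing is the clinical argument for PENG. The Summary says of LPB that "it also blocks motor fibers, leading to lower extremity weakness". If failed lifts are more common with LPB, a lower label for them lowers the LPB mean more than the PENG mean and enlarges the reported difference.

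The second issue is efficiency. The same test on the same limb is recorded before the block, but the stated comparison uses only the six-hour grade. Variation in strength that was already present before surgery stays in the error term, and any chance imbalance between arms is left uncorrected.

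**Working it through.** **The plan's own figure.** The plan states no figure for motor strength. Its only sample size is for six-hour movement pain (Power Analysis: margin 1, SD 2.0, significance level 0.05, power 80%). Two one-sided tests with true difference 0 give n = 2 × [2.0 × (1.645 + 1.282) / 1]² = 68.5, so 69 per arm. This reproduces the plan. I use 69 per arm below; nothing that follows changes it.

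**Shift from labelling grade 2.** Let p2 be the share of an arm whose true grade is 2. If each is recorded k grades too low (k = 1 for a label of 1, k = 2 for a label of 0), the arm mean falls by k × p2. The arm difference (PENG minus LPB) then moves by k × (p2 in LPB − p2 in PENG).

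The documents give no grade distribution, so both cases are assumptions. Shares are for grades 0, 1, 2, 3, 4, 5.

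- *Mild weakness.* LPB 3, 4, 8, 20, 35, 30%; PENG 1, 1, 3, 15, 35, 45%. Means are 3.70 and 4.17, difference 0.47. The shift is 1 × (0.08 − 0.03) = 0.05 or 2 × 0.05 = 0.10, so the difference becomes 0.52 or 0.57.
- *Marked weakness.* LPB 10, 15, 20, 25, 20, 10%; PENG 2, 4, 8, 20, 36, 30%. Means are 2.60 and 3.74, difference 1.14. The shift is 1 × (0.20 − 0.08) = 0.12 or 2 × 0.12 = 0.24, so the difference becomes 1.26 or 1.38.

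Power of the t-test at 69 per arm barely changes: about 69-70% throughout the mild case, and above 99% throughout the marked case. The share at grade 3 or above does not change at all: 85% v 95% in the mild case, 55% v 86% in the marked case.

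**No false difference.** If the arms have the same true grades and assessors do not know the arm, any labelling rule gives both arms the same distribution of recorded grades. The expected difference is then 0.

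**Baseline grade.** For a linear comparison, adjusting for a baseline value with correlation r to the outcome multiplies the SE by √(1 − r²). Assumed r of 0.2, 0.3 and 0.5 give 0.980, 0.954 and 0.866, that is SE reductions of 2%, 5% and 13%. This is a guide only for an ordinal model. The 95% range of chance imbalance in mean baseline grade is ±1.96 × SD × √(2/69), which is ±0.17, ±0.23 and ±0.33 for assumed baseline SDs of 0.5, 0.7 and 1.0.

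**Cost of dichotomizing.** In the mild case, comparing 85% with 95% gives SE = √[(0.85 × 0.15 + 0.95 × 0.05)/69] = 0.0504. The ratio is 0.10/0.0504 = 1.99, so power is about 51%, against 69% for the t-test on the full scale.

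**The case against.** The strongest reply is that little is at risk. Grades 0 and 1 are defined by what an assessor can see when the patient tries to lift, so only recognition of grade 2 is affected, and grades 3 to 5 remain sound. The protocol also cites a reference for the scale, and any grading instructions in it cannot be seen here. Assessors are blinded, so a mislabel follows the leg and not the arm. The t-test keeps nearly the same power. An ordinal method is not clearly more powerful either: in simulations with two other assumed pairs of distributions at 69 per arm, a rank test on merged grades had 73% and 58% power against 68% and 59% for the t-test. All of this stands. It limits the point to the size and meaning of the estimated difference, not the validity of the test.

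A reader might infer more than the documents support:

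- *That preoperative weakness biases the comparison.* Randomization makes it equal in expectation between arms. It is also measured; it is only unused in the stated analysis.
- *That many patients with stable weakness enter.* The exclusion of "presence of a progressive lower extremity neurological deficit" does not name stable weakness, but multiple sclerosis, Parkinson's disease and contraindications to regional anesthesia are also excluded, and no rate is given.
- *That LPB patients are expected to fall below grade 3.* The Summary speaks only of weakness, which fits grade 3 or 4 equally well.
- *That the LPB mean could move by 0.4 to 0.8 grade.* That needs an assumed 20-40% unable to lift, all scored 0 in one reading and all 2 in the other (0.20 × 2 and 0.40 × 2). It also ignores PENG patients who cannot lift. It is an extreme bound, not an expected effect.

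**Conclusion.** The point holds in limited form. The named manoeuvre and the definition of grade 2 do not fit together, no grading rule fills the gap, and the planned mean difference carries the ambiguity. The illustrative shift is 0.05 to 0.24 grade. It rests wholly on assumed distributions, and on failed lifts being more common with LPB. It changes the reported size of a real difference; it does not produce a false one, and the documents do not support calling the strength comparison invalid.

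Leaving out the recorded baseline grade is a loss of precision, about 2-13% of the SE for assumed correlations of 0.2 to 0.5, and not a bias. Both matters concern one secondary outcome. The pain endpoint, the equivalence test and the planned 69 (80 recruited) per arm are untouched.

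**What to change.** In Data Analysis, give six-hour strength its own sentence: compare the arms with a proportional-odds model on four ordered categories (cannot lift, grades 0-2 combined; 3; 4; 5), adjusted for the recorded baseline grade, and report the odds ratio with its confidence interval. Add the proportion at grade 3 or above in each arm, with the difference and confidence interval, as a supportive summary. It should not be the headline, because it merges grades 3, 4 and 5 and loses power.

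The cost is wording in the statistical section and loss of the 0-1-2 distinction, which the manoeuvre does not reliably provide. The bedside test, staffing and sample size stay as they are.

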### **Randomization**

Prior to beginning any regional anesthesia procedures, each patient will be randomized to one of the aforementioned treatment arms consisting of LPB or PENG block by research personnel and/or the attending anesthesiologist in charge of the patient's care. Randomization will occur in blocks of sequentially numbered opaque envelopes. Patients will be blinded to their treatment arm assignment, as will all research personnel who collect outcome data. Patient blinding will occur through the use of a sham block procedure as detailed below.

### **Interventions**

Once randomization occurs, standard American Society of Anesthesiology (ASA) monitors and supplemental oxygen will be applied to the patient, and a timeout procedure will be conducted to verify all patient data and paperwork are correct. Unless the patient has a contraindication, each patient will also receive a weight-appropriate dose of acetaminophen and celecoxib, or meloxicam (if the patient has an allergy to sulfonamide medications or to celecoxib) at this time.

All blocks will be performed by an experienced faculty anesthesiologist well versed in the performance of LPB and PENG blocks, or by a regional anesthesia fellow directly supervised by a regional anesthesia specialized faculty anesthesiologist. Sedation for block placement will be administered using midazolam and fentanyl titrated to patient comfort, at the discretion of the attending anesthesiologist performing or supervising the regional anesthesia procedures. All subjects will start in the supine position, and their relevant anatomy for PENG block will be imaged using an ultrasound as described previously, after skin preparation with chlorhexidine solution. All subjects will then receive a skin wheal using 1mL of 1% lidocaine at the skin entry site for a typical PENG block. Those subjects assigned to the PENG treatment arm will subsequently receive a PENG block using 20mL of 0.2% ropivacaine with 1:400,000 epinephrine dosed in 5mL increments with negative aspiration beforehand and between each aliquot. All subjects will then be transitioned to lateral decubitus positioning with the surgical

side up (standard at our institution, as we use an isobaric spinal solution). Using a skin marker, midline will be marked on their lumbar spine at the level of the iliac crests, and a point two thirds the distance between midline and the posterior superior iliac spine on the surgical side will be marked. Following this, their lower back areas will be prepared with antiseptic solution and draped in sterile fashion. All subjects will then receive a skin wheal with 1cc of 1% lidocaine at the standard LPB block site just marked as described above. Those subjects assigned to the LPB treatment arm will subsequently receive a stimulation-based LPB dosed with 20cc of 0.2% ropivacaine with 1:400,000 dilution epinephrine dosed in 5mL increments with negative aspiration beforehand and between each aliquot. The PENG block site skin wheal will behave as a sham block for subjects enrolled in the LPB arm, and the LPB block site skin wheal will behave as a sham block for those enrolled in the PENG arm.

All patients will then receive a spinal block as the primary anesthetic using 3.5mL of 0.5% ropivacaine with 10mcg fentanyl. Following placement of the spinal block, the patients will be brought to the operating room and receive our standard intraoperative protocol of propofol infusion for sedation, along with dexamethasone 10mg IV, ondansetron 4mg IV, surgical antibiotic prophylaxis as appropriate, and IV tranexamic acid 1g at both capsule opening and capsule closure. Any patients whose spinal block are determined to have failed, as checked prior to initiation of propofol sedation and surgical skin preparation with a pinch test on the surgical lower extremity, will be induced under general anesthesia using propofol with placement of a laryngeal mask airway or endotracheal tube at the discretion of the attending anesthesiologist.

## Materials

Ultrasound guidance for imaging the relevant anatomy for the PENG block will be obtained using curvilinear probe and a sterile probe cover. An insulated, stimulating block needle be used to perform the PENG blocks for subjects enrolled in the PENG treatment arm, as well as for the LPB for subjects enrolled in the LPB treatment arm. The entire lower back area will be prepped in sterile fashion prior to LPB and spinal block placement. All products and medications used are FDA approved for the abovementioned procedures.

## Measurements

Following the completion of surgery, all subjects will be brought to the post-anesthesia care unit (PACU) for recovery, where they will recover until satisfactory resolution of spinal block as judged by an attending anesthesiologist is shown. Subjects will then be transported to an inpatient room, where nurses will monitor their vital signs and pain scores regularly. Subjects will receive standard of care pain medications for postoperative pain management as indicated. Subjects will continue to receive scheduled acetaminophen 1000mg every six hours (or 15mg/kg if their weight is below 65kg), and the NSAID administered preoperatively (either celecoxib 200mg twice daily or meloxicam 15mg once daily) barring any contraindication such as renal impairment or vascular disease. Oxycodone every four hours may also be administered as needed with dose ranges determined by the Davie Medical Center perioperative surgical home anesthesiologist consulted for postoperative care, or another narcotic at equipotent dosages if they have a contraindication to oxycodone. Alternatively, they may receive combination products such as Percocet (oxycodone/acetaminophen) or Vicodin/Norco (hydrocodone/acetaminophen) instead, with the acetaminophen dosage adjusted accordingly. All

opioids will be converted to oxycodone equivalents to allow for appropriate comparison using a widely available dose conversion table.

Nurses will chart vital signs and medication administration in the electronic medical record (EMR) as per our standard protocol. Research personnel will measure patient-reported NRS pain scores at rest and with movement for each time by patient interaction, either face to face, or by calling the patient's room or phone numbers. This will include the primary outcome of patient-rated pain with movement of the surgical extremity on the NRS pain scale at six hours after block placement (roughly correlating to two hours after arrival to their room) as well as secondary outcomes that include but are not limited to pain at rest and with movement at 12, 18, and 24 hours following block placement, and strength to straight leg raise at six hours post-block placement. The cumulative 24 hour opioid consumption will be abstracted from the EMR for doses received while admitted, and documented by the patient in their pain journal and abstracted via phone call after their discharge, if this occurs prior to 24 hours after the block. Physical therapists will also document their encounters in the EMR, including but not limited to the secondary outcome of distance ambulated during their first session in feet. These metrics will be accessed, abstracted, de-identified, and analyzed by research personnel who are blinded to group allocation.

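### The primary 6 h movement-pain score may be taken by telephone, and nothing requires the leg to be moved when it is given, although every patient is still in hospital

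*Combined protocol and SAP*

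**What the plan says.** Under Measurements, research personnel take the NRS scores at rest and with movement at each time point, "either face to face, or by calling the patient's room or phone numbers". The following sentence reads "This will include the primary outcome of patient-rated pain with movement of the surgical extremity on the NRS pain scale at six hours", so the telephone option reaches the primary endpoint. That sentence ends its list of outcomes with "strength to straight leg raise at six hours post-block placement".

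Baseline data collection says "All patients will still be admitted at the six hour mark, for collection of the primary endpoint of NRS pain with movement", and names 6 h motor strength alongside it. The same section says strength is "assessed by straight leg raise on the surgical side to resistance and measured on the six-point Medical Research Council (MRC) scale", where "4 represents movement possible against some resistance, and 5 represents normal motor strength against resistance". It collects telephone numbers for use once the patient has gone home.

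Objectives contains the only rule for a patient who has not moved: at 18 h, the movement score is then treated as missing. No section defines the movement, asks the assessor to prompt or watch it, ties the 6 h pain score to the strength test, or asks for the mode of contact to be recorded.

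**The concern.** The primary endpoint is pain on moving the operated leg, asked about two hours after the patient reaches the room. A patient who is telephoned then, and is not asked to move, may give a score for pain at rest or for a movement that is remembered or imagined. If some scores in both arms are of this kind, and the arms are closer together at rest than on movement, the observed difference between arms is smaller than the true difference on movement.

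In a superiority trial such dilution is conservative. In this equivalence trial, with a margin of one NRS point, it works towards the hypothesis that the trial sets out to confirm. Blinding of patients and outcome assessors does not prevent it, because it needs no preference on anyone's part.

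**Working it through.** **1. The sections side by side.**

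| Question | What the plan says | Where |
|---|---|---|
| May a pain score be taken by telephone? | Yes, at each time point, including by a call to the patient's room | Measurements |
| Does this cover the primary score? | Yes, the next sentence includes it | Measurements |
| Where is the patient at 6 h? | Still admitted, in every case | Baseline data collection |
| Is anyone needed at the bedside at 6 h? | Yes, by implication: grades 3, 4 and 5 differ by response to resistance | Baseline data collection; the 0-5 scale for 6 h is in Objectives |
| Must the leg be moved for the 6 h movement score? | Not stated | – |
| What if the patient has not moved? | Rule at 18 h only | Objectives |

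The resistance wording describes the baseline test. For 6 h the plan gives only the straight leg raise and the same 0-5 scale, which implies the same examination. A call to the room can only be a call to an inpatient, so the telephone option is not confined to the period after discharge.

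**2. The plan's own sample size.** Inputs from Power Analysis: margin 1, SD 2.0, significance level 0.05, power 80%. Data Analysis specifies two one-sided t-tests. With a true difference of 0:

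n per arm = 2 × [SD × (z₀.₉₅ + z₀.₉₀) / margin]² = 2 × [2 × (1.645 + 1.282) / 1]² = 68.5, rounded up to 69.

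This reproduces the stated 69 per arm. Power from the t distribution at 69 per arm is 79.9%. The point does not alter this figure.

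**3. Illustration of the dilution.** Let f be the share of 6 h movement scores, in both arms, that in fact reflect rest pain. Then

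observed difference = (1 − f) × (difference on movement) + f × (difference at rest).

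Assume a movement difference of 1.0 (at the margin, so not equivalent), no difference at rest, and an SD that stays at 2.0. The observed difference is then 1 − f. At 69 per arm the standard error is 2 × √(2/69) = 0.34. The chance that both one-sided tests reject, so that equivalence is declared, is:

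| f | Observed difference | 69 per arm | 80 per arm |
|---|---|---|---|
| 0 | 1.00 | 5.0% | 5.0% |
| 10% | 0.90 | 8.8% | 9.2% |
| 25% | 0.75 | 18.0% | 19.5% |
| 50% | 0.50 | 42.4% | 47.1% |

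**4. Sensitivity to the rest-pain assumption.** If the arms differ by 0.5 at rest, the observed difference at f = 25% is 0.75 × 1.0 + 0.25 × 0.5 = 0.875. The error then lies between the 10% and 25% rows, nearer the former. If the arms differ as much at rest as on movement, there is no dilution.

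**The case against.** A reader might infer that the strength grade too could be taken by telephone, and so be missing or made up. The documents do not support this. The telephone clause attaches to the NRS scores, strength comes later in a loosely built list, and Baseline data collection treats it as a hands-on test in an admitted patient. The strength test matters here only because it already brings an examiner to the bedside.

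That fact also limits the concern. If someone must visit at 6 h, the pain score will often be taken then, and f may be small. The text permits a call; it does not say calls will be usual. This stands, but it reduces the risk without removing it, because the pain score is not tied to that visit.

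A reader might also assume that bedside scores are given on an observed movement and telephone scores are not. No section says so. A caller can ask the patient to move the leg, and a bedside interviewer can accept a remembered score. A face-to-face requirement alone would therefore not close the gap; the movement has to be required too.

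Finally, the dilution figures lean towards the worst case. They assume that affected scores are pure rest pain and that the arms do not differ at rest, and the plan gives no expected rest scores. Here f counts affected scores, not telephoned ones, so a given f may need a larger telephone share. Mixed collection may also widen the spread of scores, which by itself makes equivalence harder to show. The figures show direction and sensitivity; they are not a forecast.

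**Conclusion.** The point holds as a gap in the measurement rule for the primary endpoint. The plan permits a 6 h movement score by telephone and nowhere requires a movement when it is given, although an inpatient stay and a bedside examination are both in place at that time. The likely direction of any effect is towards equivalence, provided the arms differ less at rest than on movement. Its size cannot be derived from the documents, because f is unknown. Under the stated assumptions even f = 10% raises the chance of wrongly declaring equivalence at the margin from 5.0% to 8.8%. The sample size and the choice of test are unaffected. The change should be made because it is nearly free and protects the result on which the trial is decided.

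**What to change.** In Measurements, state that at 6 h the rest score, the movement score and the straight leg raise are taken face to face in one visit by the blinded assessor. Require the movement score to be rated on a movement performed at that visit; the straight leg raise already being done is one candidate. Because the Summary expects leg weakness after lumbar plexus block, also say in advance what is recorded if the patient cannot perform the movement. Keep telephone and journal collection for 12, 18 and 24 h, and record the mode of each score.

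This takes a few sentences and a mode field on the data collection form. It adds no visit, since the strength grade already needs an examiner, and the sample size does not change. The downside is that a few scores that would have been telephoned may fall slightly off the nominal 6 h.
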